6.4.8 Recurrence

Recurrence (loss of correction) is considered to have occurred at 24-months post-procedure if any two of the following 3 criteria are met: IMA of $\geq 12^\circ$, HVA $\geq 20^\circ$, TSP ≥ 4 . An alternative definition of recurrence will also be applied: HVA $\geq 15^\circ$.

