## **3.0 STUDY ENDPOINTS**

### **Primary:**

Radiographic recurrence of hallux valgus deformity at 24 months for subjects with successful correction (defined as IMA <9.0°, HVA <15.0° and TSP as ≤ 3 at 6 weeks post-Lapiplasty® Procedure). Recurrence is defined by any two of the following three criteria being met at 24 months post-procedure: IMA of ≥12°, HVA ≥20° and TSP ≥4.

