6.4.7 Correction

Successful correction is defined as any two of the following 3 criteria being met at 6 weeks post-procedure: IMA $<9.0^\circ$, HVA $<15.0^\circ$, TSP as ≤ 3 . In other words, if none or one of the measurements is out of range at 6 weeks, the foot is considered “corrected”. If two or more measurements are out of range at 6 weeks, the foot is considered “not corrected”.

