7.2.2 Secondary Effectiveness Analysis

Effectiveness analyses will be performed on the following secondary endpoints:

- 1) Percentage of subjects with recurrence at 12 months where recurrence is defined as meeting 2 of the following 3 criteria: IMA of $\geq 12^\circ$, HVA $\geq 20^\circ$ and TSP ≥ 4 .

- 2) Percentage of subjects with recurrence at 12 months and 24 months where recurrence is defined as HVA >15°.
- 3) Percentage of subjects with recurrence at 12 months and 24 months where recurrence is defined as HVA >20°.
- 4) Percentage of subjects with successful correction at 6 weeks.
- 5) Change from baseline in radiographic angular/positional alignment for HVA, IMA, TSP, and sagittal plane at 6 weeks, 4 months, 6 months, 12 months, and 24 months.
- 6) Percentage of subjects with non-union (absence of clinical/radiographic healing) at 12 months.
- 7) Time to weight-bearing in a controlled ankle motion (CAM) boot, in days.
- 8) Time to weight-bearing in shoes, in weeks.
- 9) Time to return to full unrestricted activity, in months.
- 10) Change from baseline in pain at the base of the big toe (bunion related) assessed via VAS at 0-14 days, 14-21 days, 6 weeks, 4 months, 6 months, 12 months, and 24 months.
- 11) Change from baseline in Quality of Life at 6 months, 12 months, and 24 months as measured by PROMIS-29 (for adult subjects), PROMIS-25 (for pediatric subjects), and MOxFQ (for all subjects).
- 12) Change from baseline in range of motion of the 1st MTP dorsiflexion, plantarflexion, and dorsiflexion plus plantarflexion at 4 months, 6 months, 12 months, and 24 months.
- 13) Change from baseline in foot swelling measurements at 0-14 days, 14-21 days, 6 weeks, 4 months, 6 months, and 12 months.
- 14) Summary of POSAS responses over time at 4 months, 6 months, 12 months, and 24 months.

Statistical summaries will be produced in accordance with section 7, and listings will be generated by site, subject, and visit (where applicable) within subject.

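### The HVA-only recurrence rule sits on the 6-week correction line and is not limited to feet that were below that line, so feet with no change can be counted as recurrences

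*SAP*

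**What the plan says.** SAP 6.4.8 describes recurrence as loss of correction. Its main rule needs two of three criteria at 24 months: IMA ≥12°, HVA ≥20°, TSP ≥4. It then adds: "An alternative definition of recurrence will also be applied: HVA" ≥15°. SAP 7.2.2 item 2 turns this into a secondary result with a different inequality: "Percentage of subjects with recurrence at 12 months and 24 months where recurrence is defined as HVA >15" degrees.

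The 6-week HVA limit for correction is <15.0° in both documents, but the rule around it differs. SAP 6.4.7 asks for any two of IMA, HVA and TSP, and counts a foot as corrected "if none or one of the measurements is out of range at 6 weeks". Protocol 3.0 joins the three: "IMA <9.0°, HVA <15.0° and TSP as ≤ 3 at 6 weeks".

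The protocol defines its primary endpoint as "Radiographic recurrence of hallux valgus deformity at 24 months for subjects with successful correction", and SAP 7.2.1 carries that restriction. SAP 7.2.2 item 2 does not repeat it, and SAP 7.2 makes the ITT population the default for all effectiveness analyses.

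Neither 6.4.8 nor item 2 asks for a rise from the 6-week value, a repeat read or a confirming film. SAP 6.4.3 describes reads by one type of qualified radiologist and mentions no duplicate reading. Protocol 12.1 sends only notable outliers for review.

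**The concern.** If recurrence means loss of correction, a foot has to have been corrected on the measure in question before it can recur. The HVA-only rule does not secure that, for two separate reasons.

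- **Feet never below the line.** A foot at or above 15° at 6 weeks can enter item 2 and already meets the definition, with no change and no reading error.
- **Feet just below the line.** Correction ends at the value where recurrence begins. Any non-zero reading error will move some stable feet across. The main rule is better protected: it leaves 5° between the HVA limits (15° to 20°) and 3° between the IMA limits (9° to 12°), and it needs two criteria.

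At stake is a listed secondary effectiveness result at two visits, which belongs with the recurrence proportions in Table 3. As written it would combine never-corrected feet, reading error and true loss of correction under one label. The error inflates the apparent recurrence rate.

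**Working it through.** The plan has no figure to reproduce: the sample of 200 is set without a calculation, and no expected HVA-only rate is stated.

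**Step 1: a foot that does not change (no model needed).** Take HVA 16°, IMA 7°, TSP 2 at every visit.

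- Correction, SAP 6.4.7: IMA 7 < 9.0 is met, TSP 2 ≤ 3 is met, HVA 16 < 15.0 is not. Two of three are met, so the foot is corrected.
- HVA-only recurrence at 12 and 24 months: 16 ≥ 15 and 16 > 15. Recurrent under either inequality.
- Main rule at 24 months: IMA 7 < 12, HVA 16 < 20, TSP 2 < 4. No criterion is met, so not recurrent.
- Correction, Protocol 3.0 (all three): not corrected, so excluded if the analysis were confined to corrected feet.

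**Step 2: feet near the line (assumed inputs).** Let true HVA be T ~ N(m, SD²), unchanged over time. The two reads are T + e₁ and T + e₂, with independent errors of standard deviation s. Put z = (15 − m)/√(SD² + s²) and ρ = SD²/(SD² + s²). Then

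- P(read ≥15° at 6 weeks) = 1 − Φ(z). With no true change, this is also the expected item 2 rate if every foot is included.
- P(later read ≥15° | 6-week read <15°) = [Φ(z) − Φ₂(z, z; ρ)]/Φ(z).

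Worked case, m = 9, SD = 4, s = 2: √20 = 4.47, z = 6/4.47 = 1.34, Φ(z) = 0.910, ρ = 16/20 = 0.80. The joint probability of <15° then ≥15° is 0.0403, and 0.0403/0.910 = 4.4%.

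| m, SD, s (assumed) | Reads ≥15° at 6 weeks | Reads <15° at 6 weeks, later ≥15° |
|---|---|---|
| 8, 4, 1 | 4.5% | 1.3% |
| 8, 4, 2 | 5.9% | 3.1% |
| 8, 4, 3 | 8.1% | 5.3% |
| 9, 4, 2 | 9.0% | 4.4% |
| 10, 4, 2 | 13.2% | 6.2% |
| 10, 4, 3 | 15.9% | 9.7% |
| 10, 5, 3 | 19.6% | 10.0% |

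Over m = 9–10, SD = 4–5 and s = 2–3, the ranges are 9.0–19.6% and 4.4–10.0%. In the same grid only 0.1–0.9% of feet reading <15° later read ≥20°. The effect is concentrated near the line: at s = 2, the chance of reading ≥15° is 1 − Φ((15 − T)/2), which is 6.7% at T = 12°, 15.9% at 13° and 30.9% at 14°.

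**Step 3: the inequality.** With one-decimal reads, ≥ and > differ only at exactly 15.0°. If reads were recorded in whole degrees (assumed), the m = 8, SD = 4, s = 2 rate would be 3.7% under ≥15° and 1.9% under >15°.

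**Step 4: what a minimum rise would do.** Adding a rise of at least 5° lowers the 4.4–10.0% range to 1.0–5.0%. It also loses true events. For a foot moving from 12° to 17° with s = 2, the bare threshold detects Φ((17 − 15)/2) = 84%. With the added rise, and a 6-week read <15°, detection is 52%.

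**The case against.** The strongest reply is that this is one lenient definition among several, in a single-arm and mainly descriptive study. SAP 7.2.2 also reports HVA >20° at the same two visits (item 3), the two-of-three rule at 12 months (item 1) and change in HVA at each radiographic visit (item 5). Listing 5 shows the individual measurements. No test or success criterion uses the 15° rate. This stands, and it limits the consequence: a reader can see from the other results whether HVA moved. It does not make the label on the 15° rate correct.

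A second reply is that the 16° example depends on the SAP's two-of-three rule. Under the protocol's rule, in a corrected-only analysis, that foot would drop out. That is true, but item 2 states no corrected-only limit, and the current SAP rule would admit the foot even if it did. The protocol–SAP difference in the correction rule is a separate discrepancy, and settling it would not by itself restrict item 2.

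A reader might also infer that noise equals or exceeds the recurrence the study expects, because the cited retrospective series implies 100 − 96.7 = 3.3% lost correction. The documents do not support this. They give no reader error or post-operative HVA spread; at m = 8, SD = 4 the modelled rate is 1.3% for s = 1 and passes 3.3% only for s above 2. Nor is the 3.3% like for like: it concerns three-plane correction in 61 feet at a mean of 13.5 months, with no HVA cut-off stated. If it is 2/61, its exact 95% interval is 0.4–11.3%.

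**Conclusion.** The point holds for the HVA-only secondary definition. That the two limits coincide, that item 2 has no 6-week HVA restriction, and that 6.4.8 and 7.2.2 use different inequalities can all be read from the text without assumptions. So can the miscounting of an unchanged foot at or above 15°.

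The size is conditional. It rests on normal true values, independent reading errors, no true change, and assumed means, spreads and error SDs. If the central reader's error is small and most feet end well below 15°, the noise part is minor.

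A reader might extend this to the primary recurrence criteria, or conclude that a fixed 5° rise is needed. Neither follows. The primary uses separated limits and two criteria, and nothing in the documents on the reader's repeatability supports 5°. The primary's 5° gap lies between two thresholds; it does not require any foot to rise by 5°.

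**What to change.** In SAP 6.4.8 and 7.2.2 item 2:

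1. Limit the HVA-only recurrence analysis to feet with HVA <15.0° on the 6-week central read.
2. Use one inequality, ≥15° or >15°, in both sections.
3. Show the all-feet threshold rate beside it, labelled as prevalence of HVA at or above 15° (or above 15°, to match the inequality chosen) rather than recurrence. This keeps a bare-threshold figure for comparison with other series.
4. Optionally, add a sensitivity row that also requires a minimum rise from the 6-week read. Set the minimum from the central reader's measured repeatability, and state that it lowers sensitivity to small true losses.

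Items 1 to 3 remove the never-below-the-line misclassification; they do not remove reading error, which only item 4 addresses. Protocol Appendix 4 already has the central radiologist measuring HVA at Visit 5, so items 1 to 3 need no new data. The cost is SAP wording, one extra row in Table 3, and a smaller denominator, since feet at or above 15° or without a 6-week read leave the recurrence row. Item 4 needs repeat reads if no repeatability estimate exists.

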6.4.9 Non-union

Non-union is defined as pain at the TMT joint plus one or more of the following: lucency, hardware failure, or recurrence.

7 Statistical Analysis

All continuous variables will be summarized using the following descriptive statistics: n, mean, standard deviation, median, minimum, maximum, and where appropriate 95% confidence intervals (CIs). The frequency and percentages of observed levels will be reported for all categorical measures. In general, all summary tables will be annotated with the total population size relevant to that table, including any missing observations. Data listings will be sorted by site, subject, and when appropriate by visit type within subject.

Two-sided T-tests will be generated for change from baseline analyses. P-values ≥ 0.001 will be reported to 3 decimal places; p-values less than 0.001 will be reported as “ <0.001 ”. P-values less than 0.05 will be considered statistically significant. The mean, standard deviation, and any other statistics other than quantiles, will be reported to one decimal place greater than the original data. Quantiles, such as median, or minimum and maximum will use the same number of decimal places as the original data. Estimated parameters, not on the same scale as raw observations (e.g. regression coefficients) will be reported to 3 significant figures.

7.1 Study Subjects

7.1.1 Subject Disposition

All subjects who signed informed consent will be included in the subject disposition table. The number and percentage of subjects enrolled, screened, screen failed, treated, anesthetized but not treated, completed, and discontinued (including reason for discontinuation) will be summarized. Subjects are considered enrolled in the study when they have signed an informed consent. Subjects will undergo screening procedures during the baseline visit to determine if inclusion and exclusion criteria are satisfied and the subject is eligible for the study procedure. If any eligibility criteria (including intra-operative criteria) are not satisfied, the subject will be considered a screen failure and will not be considered treated in the study. Subjects are considered treated in the study when biplanar plating at the TMT joint is complete and the incision length is confirmed to meet criteria.

7.1.2 Protocol Deviations

Protocol deviations are events occurring during the conduct of the study which are not in compliance with the protocol and for which an amendment has not been granted. Protocol deviations affecting the scientific soundness of the study or the rights, safety, or welfare of the subjects, will be reported by the principal investigator (PI), as required by the Institutional Review Board (IRB). Protocol deviations will be summarized and grouped into relevant categories for analysis and may include, but not be limited to, subjects who:

- Entered the study although they did not satisfy the eligibility criteria
- Completed incorrect version of PROMIS based on age of subject
- Did not return to protective weight-bearing activities by 3 weeks (+3 days)
- Received Lapiplasty® Procedure (or other hallux valgus procedures) on contralateral foot less than 6 months after initial Index Procedure
- Developed withdrawal criteria during the study, but were not removed from study participation

A subject for whom at least one of the aforementioned deviations is reported may be excluded from the PP population.

Minor protocol deviations will be listed by site, subject, and visit within subject.

7.1.3 Demographic, Baseline, and Intra-Operative Characteristics

The following demographic and baseline variables will be summarized in accordance with Section 7:

- Date of birth (Age)
- Sex
- Race (White, Black or African American, Asian, American Indian or Alaska Native, Native Hawaiian or Other Pacific Islander, Other)
- Ethnicity (Hispanic or Latino, Not Hispanic or Latino)
- Body Mass Index (BMI)
- Operative foot (Right, left)
- Diabetes (Yes, no)
- Labor class (Sedentary, light work, medium work, heavy work, very heavy work)
- Incision length (cm)
- Incision extended (yes/no)

7.2 Effectiveness Analysis

The ITT population will be used for all effectiveness analyses. Summary statistics will be produced in accordance with section 7.

7.2.1 Primary Effectiveness Analysis

The primary effectiveness analysis will determine the proportion of subjects with radiographic recurrence of hallux valgus deformity (bunion recurrence) at 24 months, limited to subjects with successful correction at 6 weeks. Successful correction is defined as meeting 2 of the following 3 criteria: IMA $<9.0^\circ$, HVA $<15.0^\circ$ and TSP as ≤ 3 at 6 weeks post-index procedure. Recurrence is defined as meeting 2 of the following 3 criteria at 24 months post procedure: IMA of $\geq 12^\circ$, HVA $\geq 20^\circ$ and TSP ≥ 4 .

A sensitivity analysis of the primary effectiveness endpoint will be performed using the PP population if the PP and ITT populations differ considerably.

7.2.2 Secondary Effectiveness Analysis

Effectiveness analyses will be performed on the following secondary endpoints:

- 1) Percentage of subjects with recurrence at 12 months where recurrence is defined as meeting 2 of the following 3 criteria: IMA of $\geq 12^\circ$, HVA $\geq 20^\circ$ and TSP ≥ 4 .

- 2) Percentage of subjects with recurrence at 12 months and 24 months where recurrence is defined as HVA >15°.
- 3) Percentage of subjects with recurrence at 12 months and 24 months where recurrence is defined as HVA >20°.
- 4) Percentage of subjects with successful correction at 6 weeks.
- 5) Change from baseline in radiographic angular/positional alignment for HVA, IMA, TSP, and sagittal plane at 6 weeks, 4 months, 6 months, 12 months, and 24 months.
- 6) Percentage of subjects with non-union (absence of clinical/radiographic healing) at 12 months.
- 7) Time to weight-bearing in a controlled ankle motion (CAM) boot, in days.
- 8) Time to weight-bearing in shoes, in weeks.
- 9) Time to return to full unrestricted activity, in months.
- 10) Change from baseline in pain at the base of the big toe (bunion related) assessed via VAS at 0-14 days, 14-21 days, 6 weeks, 4 months, 6 months, 12 months, and 24 months.
- 11) Change from baseline in Quality of Life at 6 months, 12 months, and 24 months as measured by PROMIS-29 (for adult subjects), PROMIS-25 (for pediatric subjects), and MOxFQ (for all subjects).
- 12) Change from baseline in range of motion of the 1st MTP dorsiflexion, plantarflexion, and dorsiflexion plus plantarflexion at 4 months, 6 months, 12 months, and 24 months.
- 13) Change from baseline in foot swelling measurements at 0-14 days, 14-21 days, 6 weeks, 4 months, 6 months, and 12 months.
- 14) Summary of POSAS responses over time at 4 months, 6 months, 12 months, and 24 months.

Statistical summaries will be produced in accordance with section 7, and listings will be generated by site, subject, and visit (where applicable) within subject.

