1.1 Objectives

- 1) To determine radiographic recurrence of hallux valgus and the timing of failure following hallux valgus correction with the Lapiplasty® Procedure.
- 2) To determine whether the Lapiplasty® Procedure effectively corrects anatomical alignment of the 1st metatarsal and sesamoids in all three planes.
- 3) To assess whether early weight-bearing (WB) after the Lapiplasty® Procedure affects the union rates or causes loss of 3-plane correction.
- 4) To evaluate the quality of life and pain scores following the Lapiplasty® Procedure.

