1.2.2 Secondary Endpoints

- 1) Change from baseline in radiographic angular/positional alignment at 6 weeks, 4 months, 6 months, 12 months, and 24 months post-Lapiplasty® Procedure.
- 2) Percentage of subjects with absence of clinical/radiographic healing, or non-union, at 12 months post-Lapiplasty® Procedure.
- 3) Clinical complications through 24-month follow-up visit due to the Lapiplasty® System Implants, the Lapiplasty® Procedure, the post-operative weight-bearing protocol or health conditions that could affect other outcome measures.
- 4) Time to start weight-bearing in boot, in days.
- 5) Time to start weight-bearing in shoes, in days.
- 6) Time to return to full unrestricted activity, in days.
- 7) Change from baseline in pain at the base of the big toe (bunion related) assessed via a Visual Analog Scale (VAS) at 0-14 days, 14-21 days, 6 weeks, 4 months, 6 months, 12 months, and 24 months.
- 8) Change from baseline in Quality of Life at 6 months, 12 months, and 24 months as measured by PROMIS-29 (for adult subjects), PROMIS-25 (for pediatric subjects), and MOxFAQ (for all subjects).
- 9) Change from baseline in range of motion (ROM) of 1st MTP dorsiflexion and plantarflexion at 12 months and 24 months.
- 10) Change, if any, in incision length during the Lapiplasty® Procedure.
- 11) Change from baseline in radiographic foot length and width at 12 months post-Lapiplasty® Procedure.
- 12) Change in swelling at 6 weeks and 4 months post-Lapiplasty® Procedure as compared to 0-14 day visit.
- 13) Change in scar quality at 4 months, 6 months, and 12 months post-Lapiplasty® Procedure.
- 14) Correlation between amount of time external positioner is actively used during Lapiplasty® Procedure with necrosis, blistering, bruising, and tissue ulceration events.

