7.5 Exploratory Analysis

Additional endpoints may be pursued at the time of analysis and will be exploratory in nature.

Quality Assurance of Statistical Programming

Clinical operations will independently validate the safety analyses (adverse events and clinical complications). A second statistician will independently reproduce the primary, secondary, health economic, and summary statistics.

To provide high quality code that is understandable and allows for reproduction of the analysis, the following points will be followed:

- The population to be used in a table or listing will be explicitly set at the start of a block of code that computes the output.
- All outputs will include the date and time that the output was generated, and the name of the code file that produced the analysis.
- At the start of any code file, there will be a set of comments that provide the following information: author, date, references to inputs and outputs, reference to any parent code file that runs the child code file.

Summary of Changes to the SAP

N/A

References

- ¹ Ranging from 3.6%-78% recurrence at an average of 2.4-14 years post-surgery.
- ² Shurnas PS, et al. Foot Ankle Int. 2009. 30: 865-872.
- ³ Jeuken RM, et al. Foot Ankle Int. 2016. 37:687-95.
- ⁴ Kim Y, et al. A New Measure of Tibial Sesamoid Position in Hallux Valgus in Relation to the Coronal Rotation of the First Metatarsal in CT Scans. Foot Ankle Int. 2015; 36:944-52.
- ⁵ Okuda R, et al. The Shape of the Lateral Edge of the First Metatarsal Head as a Risk Factor for Recurrence of Hallux Valgus. J Bone Joint Surg Am. 2007; 89:2163-72.
- ⁶ Okuda R, et al., Postoperative Incomplete Reduction of the Sesamoids as a Risk Factor for Recurrence of Hallux Valgus. J Bone Joint Surg Am. 2009; 91:1637-45.
- ⁷ Catanzariti AR, et al. J Foot Ankle Surg. 1999. 38:325-332.
- ⁸ Galli SH, et al. Foot & Ankle Orthopaedics. 2020. 5(2) 1-2.
- ⁹ Ray JJ, et al., Multicenter Early Radiographic Outcomes of Triplanar Tarsometatarsal Arthrodesis with Early Weightbearing. Foot Ankle Int. 2019; 40(8):955-960.

Table of Contents of Statistical Outputs

TLF #	Title
Table 1	Subject Disposition, ITT Population
Table 2	Demographic, Baseline, and Intra-Operative Characteristics, ITT Population
Table 3	Proportion of subjects with recurrence of hallux valgus deformity at 12- & 24- months post-procedure, ITT Population
Table 4	Proportion of subjects with successful correction at 6 weeks post-procedure, ITT Population

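### The SAP plans no analysis of Objective 1's timing of failure, and its 12- and 24-month composite recurrence rates can rest on different sets of feet

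*SAP*

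**What the plan says.** Objective 1 (SAP 1.1; the same in protocol section 2.0) is "To determine radiographic recurrence of hallux valgus and the timing of failure following hallux valgus correction with the Lapiplasty® Procedure".

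- **24-month composite (primary, SAP 7.2.1).** Recurrence is two of IMA ≥12°, HVA ≥20° and TSP ≥4, assessed "at 24 months, limited to subjects with successful correction at 6 weeks".
- **12-month composite (SAP 7.2.2 item 1).** "Percentage of subjects with recurrence at 12 months where recurrence is defined as meeting 2 of the following 3 criteria", with the same cut-offs and no mention of correction at 6 weeks.
- **HVA-only rates (items 2 and 3).** Item 2 reads "Percentage of subjects with recurrence at 12 months and 24 months where recurrence is defined as HVA >15" degrees. Item 3 is worded the same way with 20°. Neither is limited to corrected feet at either visit.
- **Population (SAP 7.2).** "The ITT population will be used for all effectiveness analyses". SAP 6.2.1 defines ITT as eligible, treated subjects, with no reference to correction.
- **Output.** Table 3 in the SAP's list of statistical outputs is "Proportion of subjects with recurrence of hallux valgus deformity at 12- & 24- months post-procedure, ITT Population".
- **Definition (SAP 6.4.8).** "Recurrence (loss of correction) is considered to have occurred at 24-months post-procedure". Only the 24-month visit is named.

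IMA, HVA and TSP are read centrally at 6 weeks and at 4, 6, 12 and 24 months (protocol Appendix 4, Visits 5 to 9). The SAP summarises them as "Change from baseline in radiographic angular/positional alignment at 6 weeks, 4 months, 6 months, 12 months, and 24 months".

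**The concern.** There are two linked gaps.

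First, an objective has no analysis. Nothing in SAP 7.2.1, 7.2.2 or the output list gives the time or visit of first failure. The time-to variables in SAP 6.4.1 name follow-up, weight-bearing and return to work as examples, but not recurrence. The two-of-three rule is never applied at 4 or 6 months, so no table classifies a failure before 12 months. Those visits matter for Objective 3, which asks whether early weight-bearing causes loss of correction. Under protocol 5.3, loading increases over this period, with shoes from the 6-week visit and low-impact exercise from the 4-month visit.

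Second, a reader will take the time course from the composite rates in Table 3, and those rates can have different denominators. An unrestricted 12-month rate mixes loss of correction with correction never achieved, while the 24-month rate contains only the former. Under-correction at surgery could then be read as early recurrence, and recurrence could appear to fall when no foot improved.

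**Working it through.** **The plan's own figures.** The SAP gives no rate, power or precision calculation for recurrence. Its Introduction cites a retrospective study with 61 feet at the 1-year endpoint, 96.7% maintained correction and 1.6% symptomatic non-union. These fit 59/61 = 96.7% and 1/61 = 1.6%, which leaves 2/61 = 3.28% lost at an average of 13.5 months.

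**Can a never-corrected foot count as recurrent?** Under SAP 6.4.7 a foot is not corrected if at least two of IMA ≥9°, HVA ≥15° and TSP ≥4 hold at 6 weeks. The recurrence rule needs two of IMA ≥12°, HVA ≥20° and TSP ≥4.
- A foot at IMA 13° and HVA 22° at 6 weeks, and unchanged since, is uncorrected and meets the recurrence rule. Literally read, it counts at 12 months and is excluded at 24.
- A foot at IMA 10°, HVA 16° and TSP 3 is uncorrected but does not meet the recurrence rule.

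So some uncorrected feet, but not all, would be counted.

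**Size.** Let u be the share not corrected at 6 weeks, f the share of those meeting the recurrence rule at 12 months, and r12 and r24 the true rates in corrected feet. The documents give none of these. I assume r12 = 1% and r24 = 3.28%. The latter borrows the cited figure, although that follow-up was nearer one year.

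12-month rate in all treated feet = (1 − u) × r12 + u × f

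Example with u = 5% and f = 50%: 0.95 × 1% + 0.05 × 50% = 0.95% + 2.50% = 3.45%.

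| u | f = 25% | f = 50% | f = 100% |
|---|---|---|---|
| 0 | 1.00% | 1.00% | 1.00% |
| 2% | 1.48% | 1.98% | 2.98% |
| 5% | 2.20% | 3.45% | 5.95% |
| 10% | 3.40% | 5.90% | 10.90% |
| 20% | 5.80% | 10.80% | 20.80% |

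Each entry would stand beside a 24-month rate of 3.28%. On one denominator the pair is 1.00% and 3.28%.

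**Break-even.** The two rates are equal when u = (r24 − r12) / (f − r12).
- r12 = 1%: 0.0228/0.24 = 9.5% (f = 25%); 0.0228/0.49 = 4.7% (f = 50%); 0.0228/0.99 = 2.3% (f = 100%). Of 200 feet, that is about 19, 9 and 5.
- r12 = 2%: 0.0128/0.23 = 5.6%; 0.0128/0.48 = 2.7%; 0.0128/0.98 = 1.3%.

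**Two sets of assumed counts for 200 feet**, each with 5 corrected feet recurrent at 12 months and 7 at 24 months:
- 10 uncorrected, 5 of them meeting the rule: (5 + 5)/200 = 5.0%, then 7/190 = 3.7%. On one denominator, 5/190 = 2.6% rises to 3.7%.
- 4 uncorrected, 2 of them meeting the rule: (5 + 2)/200 = 3.5%, then 7/196 = 3.6%. The fall disappears, although the rise is still understated, since 5/196 = 2.6%.

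**The case against.** The strongest reply is that the SAP leaves the 12-month denominator unstated and does not declare it to be all subjects. The ITT rule in 7.2 also covers the primary analysis, which is restricted all the same, and Table 3's ITT label spans both visits. Section 6.4.8 equates recurrence with loss of correction, and Objective 1 speaks of failure after correction; a foot never corrected cannot lose correction. This stands in part. The unrestricted reading is the literal one and the one a programmer would probably follow, but it is not an explicit instruction. Section 6.4.8 does not settle it, because it names only 24 months and sets no denominator for 12.

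The other replies limit the scope:
- A reader might infer that every 24-month recurrence figure is restricted to corrected feet. Only the composite is. Items 2 and 3 use the same unrestricted wording at both visits, so each is comparable with itself over time. Their weakness is that never-corrected feet count as recurrences.
- A reader might infer that Table 3 is the only output bearing on timing. Table 8 gives alignment change by visit and Listing 5 gives the radiographic measurements, from which a first failing film could be worked out. The tabulated classification is missing; the data are not.
- Item 4 and Table 4 already report the share corrected at 6 weeks, so under-correction is visible. They do not show how many of those feet are counted as recurrent.
- The study is mainly descriptive, and 12-month recurrence is in neither document's endpoint list. That lowers the stakes but leaves Objective 1 without an analysis.

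**Conclusion.** The point holds as a gap worth closing in the SAP. No planned analysis answers the timing part of Objective 1, and the composite rates at 12 and 24 months can rest on different sets of feet.

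It is tempting to conclude that the time course will be distorted, or that its direction will reverse. The documents do not support that, because they give no uncorrected share. The effect is nil if every foot is corrected, and with few uncorrected feet there is no reversal (3.5% against 3.6% above). What can be said is conditional. Recurrence is expected to be rare, about 3% in the cited study, so a small number of feet matters. At assumed true rates of 1% and 3.3%, about 2% to 10% uncorrected makes recurrence look flat or falling.

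The range also depends on which definition of correction applies. Protocol section 3.0 requires all three criteria, while SAP 6.4.7 accepts any two. The protocol's reading makes the uncorrected share at least as large. The feet it adds have only one measure out of range at 6 weeks, so they could not meet the recurrence rule on that film.

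**What to change.** In the SAP:
1. Reconcile the protocol's three-criteria and the SAP's two-of-three definitions of correction, so that the primary analysis set is fixed.
2. In 7.2.2 item 1 and Table 3, use that set for composite recurrence at every visit. Show feet not corrected at 6 weeks on a separate line, with the number meeting the recurrence cut-offs at each visit.
3. For items 2 and 3, report the corrected-at-6-weeks set alongside all treated feet. This keeps the all-treated figures.
4. Apply the two-of-three rule to the existing central reads at 4, 6, 12 and 24 months, and extend 6.4.8 to name those visits.
5. For each recurrent foot, tabulate the interval between the last clear film and the first positive one, and identify this as the analysis for the timing part of Objective 1.

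The cost is SAP wording and a few more table columns. The reported 12-month rate may change, in the first set of assumed counts from 5.0% to 2.6%. No new films or reads are needed.
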